10.0 Potential Risks and Benefits

10.1 Potential Risks

Nifedipine

The controlled and open trials with chronic dosing of nifedipine extended-release tablets in hypertension and angina patients were included in the evaluation of adverse experiences. It is noteworthy that these potential risks derived from clinical studies with chronic multiple-dose administration of nifedipine in subjects with cardiovascular (e.g. hypertension and angina) diseases.

- The most common side effect reported with PROCARDIA XL was edema which was dose related and ranged in frequency from approximately 10% to about 30% at the highest dose studied (180 mg).
- Other common adverse experiences reported in patients in a placebo-controlled trials include, headache (15.8%), fatigue (5.9%), dizziness (4.1%), constipation (3.3%), and nausea (3.3%).
- Other adverse reactions were reported sporadically with an incidence of 1.0% or less.
- Gastrointestinal obstruction resulting in hospitalization and surgery, including the need for bezoar removal, has occurred in association with nifedipine extended-release tablets, even in patients with no prior history of gastrointestinal disease.
- Cases of tablet adherence to the gastrointestinal wall with ulceration have been reported, some requiring hospitalization and intervention.

Other serious side effects reported with PROCARDIA XL (nifedipine) use were:

- **Myocardial infarction [heart attack] (4%)**
- Pulmonary edema [fluid accumulation in the lungs] (2%)
- Ventricular arrhythmias [abnormal heartbeat] or conduction disturbances (0.5%)

Omeprazole/sodium bicarbonate

Each capsule contains omeprazole and sodium bicarbonate. Subjects will be asked to consult the Investigator if on a sodium restricted diet or have Bartter's Syndrome (a rare kidney disorder) or at risk of developing congestive heart failure (CHF).

- Omeprazole/sodium bicarbonate may increase risk of getting severe diarrhea caused by an infection (*Clostridium difficile*) in intestines.
- Multiple daily doses of proton pump inhibitor medicines for a long period of time (a year or longer) may
 - Have an increased risk of fractures of the hip, wrist or spine.
 - Increase the risk of inflammation to your stomach lining.
- Possibility of vitamin B-12 deficiency if you have been on omeprazole/sodium bicarbonate for a long time (more than 3 years).
- Low magnesium can happen in some people who take a proton pump inhibitor medicine for at least 3 months.

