12.1.1 Samples to be assayed

Samples from subjects fulfilling at least one of the following criteria will be analyzed for drug concentration:

1. Subjects who complete at least two study periods.
2. Subjects who have missed samples that have been pre-determined prior to the start of bioanalytical analysis to not significantly impact the overall outcome of the study, as per BPSI PK Scientist and/or Sponsor recommendation.
3. Subjects who do not complete the study due to AE(s).

The samples from subjects who were dismissed due to non-compliance will not be analyzed.

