13.0 PHARMACOKINETIC AND STATISTICAL ANALYSIS

13.1 Pharmacokinetic Analysis Data Set

The data from the following subjects meeting one of the criteria will be included in the final PK and statistical analysis:

1. Subjects who complete at least two study periods with both test and reference administered alone; or two study periods with the same product administered with and without PPI.
2. Subjects who have missed samples that have been pre-determined prior to the start of bioanalytical analysis to not significantly impact the overall outcome of the study.

Data from subjects who were dismissed or withdrew due to AE(s) will not be included in the PK and statistical analysis. The data for these subjects will be presented separately.

Any decision for excluding data from the final data set will be provided with a detailed explanation and will be properly recorded and dated.

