13.3.1 Pharmacokinetic Analysis

Pharmacokinetic parameters will be calculated using non-compartmental analysis (NCA) method. The following PK parameters will be estimated (where possible) for nifedipine and included in the PK and statistical analysis for the subjects in the final data set:

AUC_{inf} :	Area under the concentration-time curve from time zero to infinity, calculated as $AUC_t + C_{last}/\lambda$, where C_{last} is the last measurable concentration.
AUC_t :	Area under the concentration-time curve from time zero until the last measurable concentration or last sampling time t , whichever occurs first. AUC_t is estimated using the trapezoidal method.
C_{max} :	The maximal observed plasma concentration.
$T_{1/2}$:	Terminal elimination half-life, estimated as $\ln(2)/\lambda$.
T_{max} :	Time when the maximal plasma concentration is observed.
λ :	Terminal elimination rate constant, estimated by linear regression analysis of the terminal portion of the \ln -concentration vs. time plot.

If nifedipine concentration in the subject's plasma before administering any nifedipine (i.e. pre-dose) in any given period is less than or equal to 5% of the C_{max} value for that subject in the given period, then the subject's data without any adjustments can be included in all PK measurements and calculations. If the pre-dose value is greater than 5% of the C_{max} , data from that subject may be dropped from the PK and statistical analysis based on the assessment of the pharmacokinetic scientist and sponsor. Data for subjects dropped due to higher than 5% of C_{max} pre-dose concentrations will be included in a separate appendix in the final study report.

During PK and statistical analyses, drug concentrations below the lower limit of quantitation (BLQ) of an assay will be considered as zero except when they occur between two non-BLQ concentrations where they will be considered as missing during PK calculations and estimations.

Missed samples and non-reportable concentrations (e.g. quantity not sufficient) from the analytical laboratory will be treated in the pharmacokinetic analysis as if they have not been scheduled for collection.

The λ , $T_{1/2}$, and AUC_{inf} parameters will not be estimated for plasma concentration-time profiles where the terminal linear phase is not clearly defined.

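### Section 13.1 drops every period of a subject who leaves because of an adverse event, including completed evaluable ones: a potentially informative exclusion of unknown direction and probably small size

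*Combined protocol and SAP*

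**What the plan says.** Section 13.1 opens with an inclusion rule: "The data from the following subjects meeting one of the criteria will be included in the final PK and statistical analysis". Criterion 1 reads in part: "Subjects who complete at least two study periods with both test and reference administered alone; or two study periods with the same product administered with"; its closing words, not quoted here, add the matching PPI-free period. In terms of arms, that is A+B, A+C or B+D. The next paragraph states: "Data from subjects who were dismissed or withdrew due to AE(s) will not be included in the PK and statistical analysis". It adds: "The data for these subjects will be presented separately". Nothing limits this to the affected period, and the section does not say which statement governs when both apply.

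Section 12.1.1 has the samples of subjects who stop for AEs assayed. Section 13.3.3 already expects subjects with missing cells in the ANOVA. Sections 7.1 and 7.7 rule out replacement once a subject is dosed or discontinued. No sensitivity analysis that includes AE withdrawals is planned.

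For a pre-dose concentration above 5% of Cmax, Section 13.3.1 says "data from that subject may be dropped from the PK and statistical analysis based on the assessment of the pharmacokinetic scientist and sponsor".

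**The concern.** Whether a completed profile counts should depend on whether it is valid. Here it depends on why the subject later left. Two subjects with the same three clean 48-hour profiles are treated differently if one stops for an AE and the other for personal reasons.

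The reason for leaving may be related to the quantity being estimated. Section 10.1 notes: "The most common side effect reported with PROCARDIA XL was edema which was dose related". If AEs track nifedipine exposure, or the response to the PPI, the remaining subjects are a selected group. At stake are the four planned geometric mean ratios and some precision, in a study whose purpose is to measure a PPI interaction.

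The 5% pre-dose rule raises a smaller point of the same kind. Its trigger belongs to one period, its consequence falls on the subject, and the choice is discretionary and can only be made once concentrations are known.

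**Working it through.** **1. The plan's power figure.** Inputs from Section 7.1: CV 27%, ratio 1.08, limits 80–125%, 52 completers, 2x2 crossover. Section 4.1 gives two one-sided tests at 0.05.

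- σ_w = √ln(1 + 0.27²) = 0.2653
- SE = σ_w·√(2/n) = 0.2653·√(2/52) = 0.0520
- Distance to the upper limit: (ln 1.25 − ln 1.08)/0.0520 = 0.1462/0.0520 = 2.81. Subtracting t(0.95; 50 df) = 1.68 leaves 1.13, or about 87%.

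Exact integration gives 87.0%, so at least 80% is true as a floor. At CV 30%, 52 completers still give 80.5%. Enrolment of 65 matches 52/(1 − 0.20).

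**2. Which completed comparisons the rule removes.** From the sequences in Section 5.3 and the comparisons in Section 13.3.3:

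| Sequence | Complete after 2 periods | Complete after 3 periods |
|---|---|---|
| ABCD | A/B | A/B, C/A |
| BCDA | none | D/B, C/D |
| CDAB | C/D | C/A, C/D |
| DABC | none | A/B, D/B |

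After three periods every sequence meets criterion 1 and holds two complete comparisons. After two periods only ABCD meets it. CDAB has C/D by then, but criterion 1 does not list C+D, so that subject fails criterion 1 whatever the reason for leaving. No C/A or D/B pair exists after two periods. The loss therefore falls on withdrawals after period 3, and on ABCD after period 2.

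**3. Size and direction of a shift.** The documents give no AE rate or mechanism, so these inputs are assumed: between-subject log-SD 0.4, subject-by-PPI log-SD 0.15, and AE risk of 2.5% per period at typical exposure (doubled where confined to PPI or non-PPI periods), varying with exposure to the power ±1.5. Total AE withdrawal came to 9.6–14.9%. The C/A ratio was taken as the mean within-subject log difference. Each cell shows all subjects / completed pairs kept / AE withdrawals excluded.

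| Assumed AE mechanism | True ratio 0.85 | True ratio 1.25 |
|---|---|---|
| Rises with exposure, all periods | 0.8505 / 0.8504 / 0.8504 | 1.2509 / 1.2489 / 1.2468 |
| Rises with exposure, PPI periods only | 0.8497 / 0.8467 / 0.8434 | 1.2496 / 1.2418 / 1.2329 |
| Rises with exposure, non-PPI periods only | 0.8500 / 0.8529 / 0.8562 | 1.2503 / 1.2543 / 1.2590 |
| Low exposure, PPI periods only | 0.8499 / 0.8549 / 0.8604 | 1.2495 / 1.2539 / 1.2584 |
| Unrelated to exposure | 0.8498 / 0.8498 / 0.8497 | 1.2493 / 1.2494 / 1.2494 |

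The largest shift is 1.2329/1.2496 = 0.987, or 1.3%. The part added by the rule itself is 1.2329/1.2418 = 0.993, or 0.7%. The rest comes from pairs never completed, which no analysis-set rule restores. Shifts go toward 1 in some cells, away from 1 in others, and are nil in the last row.

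**4. Precision.** In these runs 3.5–5.9% of subjects were AE withdrawals holding a C/A pair, about 2 to 4 of 65. This counts the period in which the AE arose as usable. If it is not, the unrelated scenario falls from 0.975³·0.025 + ½·0.975²·0.025 = 3.5% to ½·0.975³·0.025 = 1.2%. Keeping four extra pairs (56 instead of 52) raises power from 87.0% to 89.2%. Without them the SE is √(56/52) = 1.04 times as large.

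**5. The 5% rule.** Section 3.2 gives a washout of at least 14 days (336 h) and a mean half-life under 10 h. That is more than 336/10 = 33 half-lives, so the rule should seldom be triggered.

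**The case against.** Read in order, Section 13.1 lists criteria and then makes an exception, with a stated destination for the excluded data. The assay instruction in Section 12.1.1 fits that separate presentation. A reader might infer a contradiction, but the text reads more naturally as a carve-out that lacks a statement of precedence. That objection stands. It does not rescue the carve-out, which still selects on the reason for leaving.

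A reader might also infer that the rule pulls the PPI comparisons toward no interaction. The documents do not support this. Removing high C/A ratios lowers the estimate, which moves it away from 1 when the truth is at or below 1. The only PPI effects quoted (Section 3.1, immediate-release tablets) go opposite ways, 1.26 for AUC and 0.87 for Cmax. C/D has PPI in both arms, so losing subjects with high D exposure would raise it. Concluding no interaction also requires a 90% CI inside 80–125%, which fewer subjects make harder. The edema statement in Section 10.1 comes from chronic dosing in cardiovascular patients, whereas this trial gives single 60 mg doses to healthy volunteers.

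Larger magnitudes can be constructed. With an individual ln(C/A) SD of √2·0.2653 = 0.375, deleting exactly the top 5% or 10% of ratios multiplies the estimate by 0.96 or 0.93. That is an assumed extreme, because AE withdrawal would have to pick out precisely the highest ratios. Comparing 52 with 65 usable pairs likewise supposes that all 13 non-completers left for AEs with complete pairs.

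On the 5% rule, any such criterion needs measured concentrations. Section 13.1 also requires of exclusions: "Any decision for excluding data from the final data set will be provided with a detailed explanation and will be properly recorded and dated". Recording a choice documents the discretion but does not remove it.

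**Conclusion.** The point holds as a potentially informative exclusion of unknown direction and limited reach. As written, the rule discards valid, already assayed pairs: two planned comparisons for each AE withdrawal after period 3, and A/B for an ABCD subject who leaves after period 2. Under the assumed AE rates and mechanisms the C/A ratio shifts by at most about 1.3%, of which the rule itself adds at most about 0.7%. C/D was not simulated, and the simple paired mean stands in for the planned four-arm ANOVA.

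The loss of precision is modest and the stated power is safe. No claim of bias toward no interaction can be made from these documents. The change is worth making because the exclusion is hard to defend whichever way it acts, but it is not critical to the trial's validity. The discretionary 5% rule is a minor wording matter.

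**What to change.** In Section 13.1, replace the AE sentence with a rule that completed, evaluable periods of subjects dismissed or withdrawn for AEs enter the PK analysis under the same criteria as any other subject's. Exclude only periods whose dosing or sampling was compromised, with that decision taken before bioanalysis starts, as Section 7.7 already requires for emesis and diarrhea and Section 13.1 for missed samples. Report the present exclusion as a sensitivity analysis.

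In Section 13.3.1, replace the discretionary wording with a fixed rule, for example that a period whose pre-dose value exceeds 5% of Cmax is excluded and the subject's other periods are kept.

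The cost is a few sentences and one extra set of tables. No new samples or assays are needed, and the planned ANOVA already accommodates missing cells.

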13.2 Pharmacodynamic (PD) Analysis Data Set

The data from the following subjects meeting one of the criteria will be included in the final PD and statistical analysis:

Subjects who were dosed with SmartPill™ and have collected Gastric pH samples up to 4 hours' time point in any given period.

Any decision for excluding data from the final pharmacokinetic and pharmacodynamics data set will be provided with a detailed explanation and will be properly recorded and dated.

13.3 Analysis of Data

Pharmacokinetic, pharmacodynamic and statistical analysis will be performed on all data from all subjects in the final data set.

The PK, PD and statistical analysis will be performed at BPSI using SAS® Version 9.4. The PK, PD and/or statistical analyses outlined in this protocol may be altered with appropriate justification.

13.3.1 Pharmacokinetic Analysis

Pharmacokinetic parameters will be calculated using non-compartmental analysis (NCA) method. The following PK parameters will be estimated (where possible) for nifedipine and included in the PK and statistical analysis for the subjects in the final data set:

AUC_{inf} :	Area under the concentration-time curve from time zero to infinity, calculated as $AUC_t + C_{last}/\lambda$, where C_{last} is the last measurable concentration.
AUC_t :	Area under the concentration-time curve from time zero until the last measurable concentration or last sampling time t , whichever occurs first. AUC_t is estimated using the trapezoidal method.
C_{max} :	The maximal observed plasma concentration.
$T_{1/2}$:	Terminal elimination half-life, estimated as $\ln(2)/\lambda$.
T_{max} :	Time when the maximal plasma concentration is observed.
λ :	Terminal elimination rate constant, estimated by linear regression analysis of the terminal portion of the \ln -concentration vs. time plot.

If nifedipine concentration in the subject's plasma before administering any nifedipine (i.e. pre-dose) in any given period is less than or equal to 5% of the C_{max} value for that subject in the given period, then the subject's data without any adjustments can be included in all PK measurements and calculations. If the pre-dose value is greater than 5% of the C_{max} , data from that subject may be dropped from the PK and statistical analysis based on the assessment of the pharmacokinetic scientist and sponsor. Data for subjects dropped due to higher than 5% of C_{max} pre-dose concentrations will be included in a separate appendix in the final study report.

During PK and statistical analyses, drug concentrations below the lower limit of quantitation (BLQ) of an assay will be considered as zero except when they occur between two non-BLQ concentrations where they will be considered as missing during PK calculations and estimations.

Missed samples and non-reportable concentrations (e.g. quantity not sufficient) from the analytical laboratory will be treated in the pharmacokinetic analysis as if they have not been scheduled for collection.

The λ , $T_{1/2}$, and AUC_{inf} parameters will not be estimated for plasma concentration-time profiles where the terminal linear phase is not clearly defined.

For subjects with missing or non-reportable nifedipine concentrations for three or more of the last samples, only the C_{max} and T_{max} will be presented and included in the statistical analysis. Other PK parameters will not be reported.

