The generic nifedipine ER product which utilizes a different release mechanism could amplify or reduce such a pH dependence (e.g. osmotic pump RLD vs. matrix generic counterparts). Under the existing regulatory practice, ANDA applicants of oral ER drug products are not required to conduct BE studies comparing the generic products with the RLD in patients chronically taking PPIs or with an abnormal gastric pH. This may render these generic ER products more or less dependent on gastric pH modification, commonly occurred in patients taking concomitant PPIs for the treatment of gastric acid-related disorders. It has been noted that PPIs (e.g. lansoprazole, omeprazole, esomeprazole) and PPIs with antacids (e.g. omeprazole/sodium bicarbonate) can drastically elevate the gastric pH, thus potentially changing the equilibrium solubility of co-administered drug substances or altering their release profiles. In the case of nifedipine, clinical studies have shown that in healthy volunteers receiving a single dose of 10 mg nifedipine IR tablets, AUC and C_{max} of nifedipine after pretreatment with omeprazole 20 mg once daily for 8 days were 1.26 and 0.87 times those after pre-treatment with placebo [10-12]. This shows a potential drug-drug interaction between PPIs and nifedipine that is formulated in an immediate-release dosage form.

Whether such a pH-dependent *in vitro* dissolution behavior can translate into any difference in *in vivo* pharmacokinetics for generic nifedipine ER tablets based on a matrix design can only be evaluated in subjects with an elevated gastric pH. Additional regulatory requirements in this category of oral drug products may be warranted if such changes in PK profiles as a result of pH-dependent dissolution behaviors for matrix-based nifedipine ER tablets could affect the efficacy and safety profiles. Due to complicated release mechanisms, quality attribute profiles, and *in vivo* pharmacokinetic behaviors of ER products, FDA is assessing the need of a drug-drug interaction study between PPIs/antacids (e.g. omeprazole/sodium bicarbonate) and generic nifedipine ER products based on a formulation design which is different from that of its RLD. In so doing, FDA aims to evaluate formulation dependence of interaction with PPIs/antacids which are known to elevate gastric pH and potentially affect *in vivo* drug release. The study results will help the Agency gain a better understanding of drug-drug interaction between oral

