4.0 STUDY OBJECTIVE

4.1 Study Objective

The objective of this study is to compare pharmacokinetics of nifedipine from both generic Nifedipine oral extended-release tablets, 60 mg and reference listed drug PROCARDIA XL (nifedipine) extended-release tablets, 60 mg when co-administered with or without proton pump inhibitor (PPI)/antacid, omeprazole/sodium bicarbonate capsules 40 mg/1100 mg capsules in healthy males and non-pregnant females under fasting conditions.

The two one-sided t-tests procedure Schuirmann proposed will be used to construct the 90% confidence interval at the $\alpha=0.05$ level of significance for the ratio of geometric mean of PK parameters AUC_t, AUC_{inf} and C_{max}. The limits of the 90% confidence intervals are 80.00%-125.00% which will be used for the statistical hypothesis testing. Therefore, it consists of decomposing the interval hypotheses into two sets of one-sided hypotheses.

For the drug interaction for both test and reference products, the calculated 90% confidence interval (CI) for the ratios of geometric means for AUC_t, AUC_{inf} and C_{max} will be used for the following two PK comparisons to assess if the statistical significance of interaction effect between the product type effect (test or reference) and the effect of co-administrating PPI/antacid is or not.

- Test with PPI (Study Arm C)/Test without PPI (Study Arm A)
- Reference with PPI (Study Arm D)/Reference without PPI (Study Arm B)

Hypothesis 1.1: The hypotheses for testing of the interaction effect between Test product and the effect of co-administrating PPI/antacid are as follows:

- The null hypothesis (H01): there is statistical significance of the interaction effect if the 90% CI of the ratios of geometric means for AUC_t, AUC_{inf} and C_{max} is less than 80.00%.
- The alternative hypothesis (H11): there is no statistical significance of the interaction effect if the 90% CI of the ratios of geometric means for AUC_t, AUC_{inf} and C_{max} is greater than or equal to 80.00%.
- The null hypothesis (H02): there is statistical significance of the interaction effect if the 90% CI of the ratios of geometric means for AUC_t, AUC_{inf} and C_{max} is greater than 125.00%.

- The alternative hypothesis (H12): there is no statistical significance of the interaction effect if the 90% CI of the ratios of geometric means for AUC_t, AUC_{inf} and C_{max} is less than or equal to 125.00%.

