13.3.3 Statistical Analysis

Descriptive statistics (min, max, median, mean, standard deviation and coefficient of variability) of all PK parameters will be provided for nifedipine for all study arm groups.

ANOVA including sequence, subjects nested within sequence, period and study arm will be performed on the ln-transformed data for AUC_t , AUC_{inf} and C_{max} and on the untransformed data for T_{max} , λ and $T_{1/2}$.

T_{max} will be analyzed using an additional non-parametric test (Wilcoxon test).

The 90% CI of the ratios of geometric means for AUC_t , AUC_{inf} and C_{max} will be calculated based on the LSMEANS and ESTIMATE of the ANOVA.

The following PK comparisons will be carried out:

- Test with PPI (Study arm C)/Test without PPI (Study arm A)
- Reference with PPI (Study arm D)/Reference without PPI (Study arm B)
- Test with PPI (Study arm C)/Reference with PPI (Study arm D)
- Test without PPI (Study arm A)/Reference without PPI (Study arm B)

For Pharmacodynamic Data:

The descriptive statistics (min, max, median, mean, standard deviation and coefficient of variability) of the gastric pH and change of gastric pH will be calculated for both test and reference products.

Analysis of Variance (ANOVA) for gastric pH and change of gastric pH from baseline will be carried out.

The following gastric pH comparisons will be carried out:

- Study arm C PPI (Day7) – Study arm A (Day2)

- Study arm D_{PPI (Day7)} – Study arm B_(Day2)
- The comparison of the change between test and reference can be assessed

Additional statistical and alternate tests will be performed if necessary.

Missing data will not be included in the statistical analysis. There are potential two kinds of unbalanced designs for the analysis: (1) unequal number of subjects across groups, (2) missing cells: there are not available data for some subjects. The Type 3 method will be used for the calculation of sums of squares using SAS software. All the fixed effects will be tested using the Type 3 in the ANOVA to detect statistically significant differences ($\alpha=0.05$) if applicable. A mixed effects ANOVA model for gastric pH with fixed factors of sequence, period, and study arm and random effects of subject will be fit. A compound-symmetric or other appropriate covariance structure will be used in the analysis.

The null hypotheses for gastric pH comparisons for different study arms are:

- For the comparison of Study Arm A and Study Arm C

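### The 80-125% criterion covers only total and peak exposure, so a pH effect confined to the first hours, above all slower release, can leave every equivalence measure within limits

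*Combined protocol and SAP*

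**What the plan says.** Section 3.1 gives the reason for the study. In-house dissolution testing found a matrix generic to be pH-dependent and the osmotic reference not, and "FDA aims to evaluate formulation dependence of interaction with PPIs/antacids which are known to elevate gastric pH". The same section leaves the direction of any effect open.

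Section 4.1 sets the decision rule: "The limits of the 90% confidence intervals are 80.00%-125.00% which will be used for the statistical hypothesis testing". Sections 4.1 and 13.3.3 apply it to AUCt, AUCinf and Cmax for C/A, D/B, C/D and A/B.

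Section 13.3.1 introduces its six parameters with "The following PK parameters will be estimated (where possible) for nifedipine and included in the PK and statistical analysis". The windows of the three that carry the limits are defined there:
- AUCt: "Area under the concentration-time curve from time zero until the last measurable concentration or last sampling time"
- AUCinf: "Area under the concentration-time curve from time zero to infinity"
- Cmax: "The maximal observed plasma concentration", whenever it occurs

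Tmax has an ANOVA and a Wilcoxon test (13.3.3). It has no equivalence limit and appears in no hypothesis of section 4.1. No partial AUC is listed.

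Much of the data collection falls in the early hours. Blood is drawn hourly from 1 to 10 h (5.1, 8.7), gastric pH is recorded over 8 h (3.3, 8.4), and the fast lasts 6 h after dosing, with the first meal at about 6.5 h (8.2).

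**The concern.** The mechanism under study is a change in release while the tablet meets raised gastric pH. If that effect is limited to the first hours, drug not released early may be released later. Total AUC then recovers, and a Cmax reached later in the profile moves little. A result inside 80-125% on all three measures would support comparable total and peak exposure, but would say little about whether early release had changed. The blood samples needed to show this are already planned, but no pre-specified parameter summarises them.

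**Working it through.** **The plan's own figure.** Section 7.1 assumes a 2x2 crossover, CV 27%, ratio 1.08 and at least 52 completers.
- s_w = √ln(1 + 0.27²) = 0.265; SE = 0.265 × √(2/52) = 0.052.
- Power of the two one-sided tests at 0.05 each is 87% at N = 52 and 93% at 65-66. The stated minimum of 80% holds, and the sample size is not in dispute.

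**One case by hand (assumed inputs).** One compartment, zero-order release over 16 h, half-life 4 h, so k = ln 2/4 = 0.1733/h. Release is halved for the first 2 h, then runs at the normal rate until the dose is out (17 h). Concentrations are in units of R/(kV), with R the release rate and V the volume.
- Cmax, at the 16 h sample. Undisturbed: 1 − e^(−16k) = 0.9375. Deficit: 0.5 × (e^(−14k) − e^(−16k)) = 0.5 × (0.0884 − 0.0625) = 0.0129. Ratio = 0.9246/0.9375 = 0.99.
- AUC0-6h. Undisturbed: 6 − (1 − e^(−6k))/k = 6 − 3.7305 = 2.2695. Deficit: 0.5 × [2 − (1 − e^(−2k))/k + (1 − e^(−2k))(1 − e^(−4k))/k] = 0.5 × [0.3098 + 0.8451] = 0.5775. Ratio = 1 − 0.5775/2.2695 = 0.75.
- Total AUC = dose/clearance. The whole dose is still released, so the ratio is 1.00.

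**Range.** The same model was run at the 17 protocol times with linear trapezoids. Release was zero-order over 16 or 20 h, or first-order at 0.10-0.25/h; half-life was 2, 4 or 7 h. Each entry is the ratio to the undisturbed profile.

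| Early release | Shape | AUCt | Cmax | AUC0-6h | AUC0-4h |
|---|---|---|---|---|---|
| Halved, 2 h | zero-order | 0.98-1.00 | 0.97-1.00 | 0.74-0.76 | 0.63-0.65 |
| Halved, 2 h | first-order | 1.00 | 0.96-0.99 | 0.76-0.83 | 0.66-0.71 |
| Halved, 1 h | both | 0.99-1.00 | 0.99-1.00 | 0.86-0.92 | 0.79-0.85 |
| ×0.75, 1-3 h | both | 0.98-1.00 | 0.93-1.00 | 0.82-0.96 | 0.77-0.93 |
| Doubled, 2 h | zero-order | 0.95-0.99 | 0.96-1.00 | 1.47-1.53 | 1.70-1.73 |
| Doubled, 2 h | first-order | 0.99-1.01 | 1.04-1.40 | 1.23-1.41 | 1.40-1.60 |
| Doubled, 3 h | zero-order | 0.96-0.99 | 1.00-1.30 | 1.68-1.73 | 1.92-1.93 |
| Doubled, 3 h | first-order | 0.99-1.01 | 1.10-1.53 | 1.29-1.53 | 1.47-1.72 |

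The AUCt ratios below 1 come from the sparse late sampling, since the true total is unchanged in this model. With release halved for 2 h, Tmax stays at the same sample in all zero-order cases and moves 1-2 h later in the first-order cases. With release doubled, Tmax moves earlier in every case.

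**Wider grid.** This set has 192 assumed scenarios: an absorption step of 1/h; release multiplied by 0.5, 0.7, 1.5 or 2 for 1, 2 or 4 h; zero-order over 16 or 24 h with the missed dose released later, spread out or lost, or first-order; half-life 2 or 7 h.
- In 151 of 192, all three true ratios lie within 80-125% while AUC0-4h lies outside. In 134 of those, each measure taken singly has at least an 80% chance of passing at N = 52 and CV 27%.
- All 96 slower-release scenarios keep the three true ratios within limits. With release halved for 2 h, the lowest single-measure chance of passing is 91%.
- The 9 scenarios with a planned ratio out of limits all have release doubled for 4 h: 8 through Cmax (1.33-1.48) and 1 through AUC alone (about 1.25).

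These counts depend on the grid chosen and are not probabilities.

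**The case against.** The strongest objection is about shape and direction. Section 3.1 ascribes zero-order release to osmotic systems, and the pH-sensitive product is the matrix tablet, whose release is diffusion-driven. Section 3.1 also calls nifedipine a weak acid with pKa 3.9, which would suggest faster release at raised pH. Faster release is what Cmax and Tmax detect best. This stands in part. A reader might infer that any early pH effect would pass unseen, and the documents do not support that: Tmax is tested and shifts in every doubled-release case, and Cmax can exceed 1.25. But section 3.1 leaves the direction open, and the result for slower release also holds under first-order shapes.

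Second, the chosen measures fit section 4.1, which concerns exposure, and section 3.2 justifies AUC and Cmax on that ground. No hypothesis claims an absence of effect on release. This stands, so AUCt, AUCinf and Cmax should remain as they are.

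Third, total AUC may not be insensitive in practice. For an immediate-release tablet, section 3.1 cites AUC at 1.26 and Cmax at 0.87 after omeprazole. That data point cannot settle behaviour of an extended-release tablet, but it does mean that a PPI effect on total AUC is not excluded.

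Fourth, sections 13.3 and 13.3.3 permit altered or additional analyses. They name no measure or window, so one chosen after seeing the profiles would be post hoc.

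**Conclusion.** The point holds in a limited form. No measure with an equivalence limit isolates early exposure, and a pH effect confined to the first hours can leave AUCt, AUCinf and Cmax within 80-125%. The gap is widest for slower release. With release halved for 2 h, the planned ratios stay at 0.96-1.00 while AUC0-6h is 0.74-0.83 and AUC0-4h 0.63-0.71.

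These figures rest on assumed release shape, half-life, duration of the gastric effect and effect size. Action limited to the stomach, with the remaining dose released normally afterwards, is also an assumption.

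Two stronger inferences are not supported. The first is that the trial would reach a false conclusion of no interaction: the documents do not give the effect size or direction needed to say so. The second is that AUC0-6h would catch every early change: slowing to 0.75 of normal for 1-3 h, or halving for only 1 h, leaves it at 0.82-0.96. This is an improvement the plan should make, and it does not invalidate the planned analysis.

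**What to change.** In sections 13.3.1 and 13.3.3, pre-specify partial AUC from 0 to 6 h after nifedipine as a secondary, supportive parameter. The window is the protocol's own post-dose fast and is sampled hourly.

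- Analyse it ln-transformed in the same ANOVA, and report geometric mean ratios with 90% CIs for C/A, D/B, C/D and A/B.
- State in advance how a zero partial AUC is handled. Section 13.3.1 sets BLQ values to zero, so a profile with all early values BLQ has no logarithm. Dropping such profiles would remove the slowest-release cases.
- Leave AUCt, AUCinf, Cmax, their criteria and the sample size unchanged.
- Word conclusions from those three as total and peak exposure, and report early exposure from AUC0-6h beside them.

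AUC0-6h should not be a pass/fail gate, because its within-subject CV is not given. At 52 completers and a true ratio of 1.05, power to meet 80-125% would be about 95% at CV 27%, 82% at 35%, 59% at 45% and 27% at 60%. As an estimate it remains useful. At CV 45% the 90% CI factor is exp(1.676 × 0.429 × √(2/52)) = 1.15, so an observed ratio of 0.75 would have an interval of about 0.65 to 0.86.

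The cost is protocol wording and one more parameter to program and report. No extra blood is drawn. The downside is a probably wider CI than for AUCt.
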